9.3 SAMPLE SIZE

Patients will be treated with PM060184 to test the null hypothesis (H0) that 30% or less patients are alive and free of progression at twelve weeks (PFS3) according to RECIST v.1.1 ($p \leq 0.30$) versus the alternative hypothesis (H1) that 50% or more patients are alive and free of progression at 12 weeks according to the aforementioned criteria ($p \geq 0.50$). The variance of the standardized test is based on the null hypothesis. The type I error (alpha) associated with this one-sided test is 0.025 and the type II error (beta) is 0.1; hence, statistical power is 90%.

Sixty evaluable patients are necessary to test the hypothesis. A futility analysis using O'Brien-Fleming boundaries is planned when 24 patients can be evaluated (first stage). If there are seven or more patients achieving PFS3 in the first stage then the trial will proceed to a second stage and a total of 60 patients will be recruited.

If at least 25 of 60 evaluable patients are alive and free of progression at 12 weeks then the null hypothesis can be rejected and PM060184 considered active and deserving potential development in this setting.

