9.9 METABOLOMICS (BIOMARKERS) ANALYSIS

Patients' pretreatment metabolic profile will be evaluated to search for systematic variations that may serve as biomarkers of PK, safety and/or efficacy response to treatment with PM060184. Systematic variations in the metabolic profile will be compared among patients with differences in any of these responses. Particular attention will be given to specific metabolic patterns observed in patients who develop PN associated with PM060184.

Metabolite extraction will be accomplished by fractionating the serum sample (19). Briefly, an ultra performance liquid chromatography (UPLC)-single quadrupole-MS amino acid analysis system will be combined with two separate UPLC-time-of-flight-MS based platforms analyzing methanol and chloroform/methanol serum extracts.

Data will be processed using the TargetLynx application manager for MassLynx 4.1 software (Waters Corp., Milford, USA). A set of predefined retention time and mass-to-charge ratio pairs (R_t - m/z), corresponding to metabolites included in the analysis will be fed into the program. Normalization factors will be calculated for each metabolite (20).

The metabolomics data analysis will include univariate and multivariate data analysis, with pathway mapping tools and visualization capacities to facilitate result interpretation.

Principal component analysis (PCA; non-supervised) and orthogonal partial least-squares to latent structures (OPLS; supervised) multivariate methods will be used to reduce the dimensionality of the complex data set to enable easy visualization of any metabolic clustering in samples from patients sharing a common outcome.

Among univariate data analysis, a Shapiro-Wilk test (to test the normality of data), a Student's t-test and a Wilcoxon signed-rank test, an analysis of variance (ANOVA) and a Tukey's HSD (Honestly Significant Difference) *post hoc* test will be used.

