9.10 PHARMACOGENETICS ANALYSIS

In order to explore factors that may help explain individual variability in the main PK parameters and safety outcomes, the presence or absence of germline mutations or polymorphisms will be analyzed in leukocyte DNA extracted from a blood sample obtained preferably before treatment start (along with PK sample #1 and the first metabolomics sample of Cycle 1). The influence of known polymorphisms on main PK parameters or safety outcomes will be assessed by a Student's test or a Mann-Whitney's U test as appropriate.

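### Protocol 9.9 names no method that accounts for time on treatment when it relates metabolites to peripheral neuropathy, so a marker of early progression can look like a protective neuropathy marker

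*Protocol*

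**What the plan says.** Protocol 9.9 evaluates the pretreatment metabolic profile as a source of biomarkers of PK, safety and efficacy response. Its comparison is stated as: "Systematic variations in the metabolic profile will be compared among patients with differences in any of these responses". One safety outcome is singled out: "Particular attention will be given to specific metabolic patterns observed in patients who develop PN associated with PM060184".

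The univariate methods, besides a normality test, are "a Student's t-test and a Wilcoxon signed-rank test, an analysis of variance (ANOVA") and Tukey's post hoc test. The multivariate methods are PCA and OPLS, used to show clustering of patients with the same outcome. The section mentions no time-to-event model, no landmark and no adjustment for cycles, dose or time on treatment.

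Three other places bear on this:

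- Protocol 5.3 and 6.3.2: treatment continues until progression, unless toxicity, refusal or another listed reason ends it sooner.
- Protocol 8.5.1: adverse events are collected until 30 days after the last dose, or until new antitumor therapy if that comes first.
- SAP 8.7 and 8.9: the pharmacogenetic and metabolomic analyses are left to separate documents.

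For pharmacogenetics, Protocol 9.10 says: "The influence of known polymorphisms on main PK parameters or safety outcomes will be assessed by a Student's test or a Mann-Whitney's U test".

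**The concern.** The question of interest is whether a metabolite changes the risk of PN at a given exposure. Comparing patients who had PN with patients who did not answers a different question, because the no-PN group mixes two kinds of patient: those who tolerated long treatment, and those who progressed before PN could appear. Under the protocol's own hypotheses, 50% to 70% of patients have progressed or died by Week 12, so the second kind is common.

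A pretreatment metabolite that reflects only tumor burden or prognosis will then differ between the groups. The false association is inverse: high values go with early progression, hence with no PN, and look protective. Conversely, a metabolite that raises PN risk and also shortens PFS has its two effects cancel.

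This is confounding by exposure. Correcting for multiplicity or overfitting does not remove it. At stake is which candidate biomarkers are taken forward for PN, which Protocol 1.2.2 calls the principal dose-limiting toxicity.

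**Working it through.** **The plan's own figure.** The only sample size and error rates given are for PFS3 (Protocol 9.3): "The type I error (alpha) associated with this one-sided test is 0.025", power 90%, null 30%, and an alternative of "50% or more patients are alive and free of progression at 12 weeks". With the null variance in the test:

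n = [1.960 × √(0.3 × 0.7) + 1.282 × √(0.5 × 0.5)]² / 0.20² = (0.898 + 0.641)² / 0.04 = 59.2, rounded up to 60.

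The stated 60 reproduces. No size or power is stated for metabolomics. Exploratory comparisons use a 0.05 level (Protocol 9.4).

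**Time on treatment.** Assume exponential times. A 12-week rate of 0.50 gives a stopping hazard λ = −ln(0.50)/12 = 0.0578 per week (median 12 weeks, about 2.8 months). A rate of 0.30 gives 0.1003 per week (median 6.9 weeks).

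**PN rate.** The documents give only a dose-limiting-toxicity figure (6% at doses above the recommended dose), so this is assumed. For example, 40% by Week 12 of continuous treatment gives μ = −ln(0.60)/12 = 0.0426 per week.

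**Mechanism by hand.** With both hazards constant, the chance of PN before stopping is μ/(μ + λ). Let the marker leave μ alone and multiply λ by the hazard ratio (HR) per SD:

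| Marker | λ, HR 1.5 | PN seen | λ, HR 2.0 | PN seen |
|---|---|---|---|---|
| −1 SD | 0.0385 | 53% | 0.0289 | 60% |
| mean | 0.0578 | 42% | 0.0578 | 42% |
| +1 SD | 0.0866 | 33% | 0.1155 | 27% |

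The weekly PN risk is identical in every row. Only the time at risk differs.

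**Simulated false-positive rate.** Conditions: n = 60, a standard normal marker with no effect on PN, and a two-sided 5% t-test of patients with PN against patients without.

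- A: median 2.8 months on treatment, minimum six weeks; PN hazard 0.05 to 0.2 per month, or Weibull shape 3 with median 3 or 5 months.
- B: 12-week PFS 0.30 or 0.50; PN 20% or 40% by Week 12; constant hazard or Weibull shape 2; treatment capped at 52 weeks.
- C: progression found only at six-weekly scans, and PN counted until 30 days after stopping.

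| Setting | HR 1.5, constant | HR 1.5, rising | HR 2.0, constant | HR 2.0, rising | Cox |
|---|---|---|---|---|---|
| A | 19–24% | 48–56% | 43–55% | 88–91% | 4–6% |
| B | 18–31% | 43–48% | 43–64% | 81–89% | 5–7% |
| C | 11–17% | 26–35% | 22–35% | 55–72% | 4–7% |

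Cox here models time to PN, censored when observation ends. At HR 1.0 the t-test rejects about 5% of the time. In setting A at HR 1.3 it rejects 11–13% (constant) and 23–30% (rising). With 24 patients (stop after stage 1; setting B, constant hazard) it rejects 10–14% at HR 1.5 and 19–29% at HR 2.0. In setting B, 94% to 100% of the false signals at HR above 1 were in the protective direction.

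**Masking.** Take a true PN marker (PN HR 1.8 per SD) in setting A with constant hazard. T-test power is 56% if the marker does not affect PFS. It falls to about 29%, 16% and 6% when the marker's PFS hazard ratio is 1.3, 1.5 and 2.0. Cox has 68% with no PFS effect and 61% at a PFS hazard ratio of 2.0.

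**The case against.** **The split is not written.** Protocol 9.9 never says that patients with and without PN will be compared by t-test. It speaks of differences in responses generally, and its list of methods is open. The signed-rank test is a paired test that suits the planned within-patient changes, and the t-test beside it could be paired too. This stands as a caution. Still, the section compares patients by response and singles out those who develop PN, so a grouped comparison is the natural reading, and nothing named there would handle exposure.

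**The details are deferred.** Silence in a summary section is not a decision to ignore exposure, and the separate plan may deal with it. That is fair. But the protocol does name its tests, and a later plan will inherit them unless told otherwise. Protocol 9.11 names Cox regression for its own time-to-event outcomes, so the sponsor does name such methods elsewhere.

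**The figures are assumed.** This stands. The PN rates, hazard shapes and marker effects are not in the documents. Counting PN for 30 days after stopping lowers the HR 2.0 rates in setting A to 34–42% (constant) and 67–86% (rising). The excess shrinks but does not vanish.

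**Protocol 9.10 is different.** This also stands. There genotype defines the groups and the PK or safety measure is compared. With a binary marker (30% carriers, assumed) in setting A, rejection is 5–8% at a carrier HR of 1.5 and 7–14% at 2.0 under constant hazard, and 14–15% and 34% under rising hazard. Any excess arises only if the polymorphism is related to time on treatment.

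**Conclusion.** The point holds as an omission in Protocol 9.9 that should be corrected. The named methods do not account for time on treatment or cumulative dose, exposure ends at progression, and a purely prognostic metabolite can therefore show a false, inverse association with PN.

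Over the three settings, the false-positive rate at n = 60 is 11% to 31% (HR 1.5) and 22% to 64% (HR 2.0) with a constant PN hazard, and 26% to 56% and 55% to 91% with a rising one, against a nominal 5%. In setting C, the most cautious, the ranges over both hazard shapes are 11% to 35% and 22% to 72%. All of this is conditional on the assumed PN rates and marker effects, and on a comparison of patients with and without PN.

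A reader might infer that every metabolite predicting early progression will be declared a PN biomarker. The documents do not support that: the rejection rates are well short of certainty, no rule for declaring a biomarker exists, and the stated aim is a search for potential markers. Nor can these magnitudes be carried over to Protocol 9.10. The analysis is exploratory, drives no trial decision and leaves PFS3 untouched.

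**What to change.** In Protocol 9.9 and the separate metabolomics plan (SAP 8.9):

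- Make the inferential analysis for PN a Cox model for time, or cumulative mg/m², from first dose to first treatment-related PN of a fixed grade, with the pretreatment metabolite as covariate. Entry criteria allow residual grade 1 neuropathy, so define the event as a rise above baseline.
- Censor at end of treatment: last dose plus 30 days, or new antitumor therapy or death if earlier.
- For the Cycle 1 Day 8 and Cycle 2 Day 8 samples, start the clock at the sample (landmark) and include only patients still free of the event.
- Keep t-test, ANOVA and OPLS comparisons by PN group as descriptive.

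In Protocol 9.10 and the plan under SAP 8.7, use the same model with genotype as covariate for exposure-dependent safety outcomes such as PN.

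The cost is wording and some programming. AE onset dates and dosing dates are collected, and the SAP already derives time on treatment and cumulative dose (in mg, so mg/m² also needs the recorded BSA). The price is reliance on proportional hazards, and on censoring being unrelated to PN risk once the marker is in the model.

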7.9 METABOLOMICS

Metabolomics (the determination of endogenous low-molecular-weight molecules or metabolites in a body fluid and their changes as a consequence of stimuli such as medical interventions), is currently being used to evaluate the efficacy and safety of medical interventions in cancer ([11](#)), thus allowing for the discovery of predictive biomarkers of drug response ([12](#)).

The metabolomics of PM060184 will be characterized by evaluating systemic variations in pre- and post-treatment metabolic profile to identify potential biomarkers of PK, safety and/or efficacy response to PM060184.

Three blood samples are required for this analysis. Patients will have one blood sample collected before each drug administration on Day 1 and Day 8 of Cycle 1, and also on Day 8 of Cycle 2, to evaluate the pretreatment profile of endogenous metabolite levels and changes after PM060184 treatment.

Blood must be collected without anticoagulant and with a separating gel, allowed to clot, and centrifuged. Serum will be collected and stored. The samples should be frozen at -80°C within 24 h. If not possible, they can be frozen at -20°C , but only for a maximum period of two weeks before shipping in dry ice to the central laboratory.

The required procedures for the collection, processing and storage of the sample for metabolomics are described in more detail in the laboratory manual. Please read it carefully before sample extraction.

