9.2 SECONDARY ENDPOINTS

- Overall Survival (OS), defined as the time from the first day of treatment to the date of death or last contact.
- Progression-free Survival (PFS), defined as the time from the first day of study treatment to the day of assessment of progression, death or last tumor evaluation.
- Overall Response Rate (ORR), defined as the percentage of patients with objective response (OR), either complete response (CR) or partial response (PR) according to the RECIST v.1.1.
- Duration of Response (DOR), defined as the time between the date when response criteria (PR or CR, the first to be reached) are fulfilled and the first date when PD, recurrence or death is objectively documented.
- Treatment safety, including AEs, SAEs, and laboratory abnormalities graded according to NCI-CTCAE v.4. Dose reductions or delays required due to treatment-related AEs, and reasons for treatment discontinuations will also be analyzed.
- Profiles of peripheral neuropathy and quality of life as reported by patients using the EORTC QLQ-CIPN20 and QLQ-C30.
- Pharmacokinetics (PK) parameters will be evaluated in plasma by population PK modeling and/or standard non-compartmental analysis.
- Metabolomics of PM060184, i.e., intra- and inter-patient systemic variations in the patient's pretreatment metabolic profile.
- Pharmacogenetics (PGt) of PM060184 will be evaluated to identify the presence or absence of germline mutations or polymorphisms that may help explain individual variability in the main PK parameters and safety outcomes.

- Pharmacogenomics (PGx) of PM060184 will be evaluated to determine predictive/prognostic markers of response and/or resistance to PM060184 (including BRAF-mutant-like gene expression subtypes).

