3.3. Endpoints

Primary endpoint:

- Progression-free survival rate at twelve weeks, defined as the rate estimate of the percentage of patients who are alive and progression-free at 12 weeks (~3 months) after the first treatment administration.

Secondary endpoints:

- Overall Survival (OS), defined as the time from the first day of treatment to the date of death or last contact.
- Progression-free Survival (PFS), defined as the time from the first day of study treatment to the day of assessment of progression, death or last tumor evaluation.
- Overall Response Rate, defined as the percentage of patients with objective response (OR), either complete response (CR) or partial response (PR) according to the Response Evaluation Criteria in Solid Tumors (RECIST) v.1.1.
- Duration of Response, defined as the time between the date when response criteria (PR or CR, the first to be reached) are fulfilled and the first date when PD, recurrence or death is objectively documented.

- Treatment safety, including Adverse Events (AEs), Serious Adverse Events (SAEs), and laboratory abnormalities graded according to National Cancer Institute Common Terminology Criteria for Adverse Events (NCI-CTCAE) v.4. Dose reductions or delays required due to treatment-related AEs, and reasons for treatment discontinuations will also be analyzed.
- Profiles of peripheral neuropathy and quality of life as reported by patients using the EORTC QLQ-CIPN20 and QLQ-C30.
- Pharmacokinetics parameters will be evaluated in plasma by population PK modeling and/or standard non-compartmental analysis.
- Metabolomics of PM060184, i.e., intra- and inter-patient systemic variations in the patient's pre- and post-treatment metabolic profile.
- Pharmacogenetics of PM060184 will be evaluated to identify the presence or absence of germline mutations or polymorphisms that may help explain individual variability in the main PK parameters and safety outcomes.
- Pharmacogenomics of PM060184 will be evaluated to determine predictive/prognostic markers of response and/or resistance to PM060184 (including BRAF-mutant-like gene expression subtypes).

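### Protocol 9.2 and 9.9 put the metabolomics endpoint on the pretreatment profile against a pre/post objective, and neither document states validation for OPLS or control across metabolites

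*Protocol*

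**What the plan says.** **Endpoint.** Protocol 9.2 lists "Metabolomics of PM060184, i.e., intra- and inter-patient systemic variations in the" patient's metabolic profile, and qualifies that profile as pretreatment. Section 9.9 opens in the same way: the patients' "pretreatment metabolic profile will be evaluated to search for systematic variations that may serve as biomarkers" of PK, safety or efficacy response. SAP 3.3 gives the same endpoint on the "pre- and post-treatment metabolic profile". Protocol 7.9 takes blood before dosing on Day 1 and Day 8 of Cycle 1 and on Day 8 of Cycle 2, "to evaluate the pretreatment profile of endogenous metabolite levels and changes after PM060184 treatment".

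**Methods.** Section 9.9 states that PCA (unsupervised) and "orthogonal partial least-squares to latent structures (OPLS; supervised) multivariate methods will be used to reduce the dimensionality" of the data, "to enable easy visualization of any metabolic clustering in samples from patients sharing a common outcome". The univariate list runs from Shapiro-Wilk and Student's t to a "Wilcoxon signed-rank test, an analysis of variance (ANOVA) and a" Tukey HSD post hoc test. "A set of predefined retention time and mass-to-charge ratio pairs" is to be loaded into the software, but the number of metabolites is not given. Section 9.9 sets no significance level of its own; Protocol 9.4 puts exploratory comparisons at 0.05. SAP 8.9 leaves the metabolomics analysis to a separate document, which it does not name.

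**The concern.** There are two separate problems.

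First, the two protocol sections that define and analyse this endpoint describe something other than the objective. Only the Cycle 1 Day 1 sample is pretreatment, and one sample cannot show intra-patient variation. Read literally, 9.2 and the opening of 9.9 give the Day 8 samples no role and do not answer the question for which they are drawn.

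Second, OPLS uses the outcome labels to choose its axes. With many metabolites and few patients, a plot of the fitted scores shows groups apart even when no metabolite is related to outcome. Per-metabolite tests at a nominal level add false leads in proportion to the number of metabolites. Section 9.9 singles out neuropathy for particular attention, so an apparent neuropathy or efficacy signature could be carried into later work on the strength of a plot.

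**Working it through.** **1. The passages side by side**

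| Place | Profile described |
|---|---|
| Protocol 9.2 (endpoint) | Pretreatment, yet intra- and inter-patient |
| Protocol 9.9, first sentence | Pretreatment |
| Protocol 9.9, univariate tests | Includes a paired test (Wilcoxon signed-rank) |
| Protocol synopsis (endpoint) | Pre- and post-treatment |
| Protocol 3 and SAP 3.2 (objective) | Pre- and post-treatment |
| Protocol 1.3 (rationale) | Before compared with after |
| Protocol 7.9 (sampling) | Baseline and change |
| SAP 3.3 (endpoint) | Pre- and post-treatment |

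The first two rows conflict with all the others, and 9.2 and 9.9 each conflict with themselves. If 60 patients gave all three samples there would be 3 × 60 = 180, of which 2 × 60 = 120 are Day 8 samples without a stated role under the literal wording.

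**2. Inputs for the noise check**

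- *Patients.* The plan gives no figure for metabolomics; the trial size of 60 (Protocol 9.3) is the stated number that enters. It reproduces: n = [(1.960·√(0.30·0.70) + 1.282·√(0.50·0.50)) / 0.20]² = [(0.898 + 0.641) / 0.20]² ≈ 59.2, rounded up to 60. If the trial stops after the first stage, n = 24.
- *Outcome split.* 30/30 (the 50% rate of the alternative hypothesis) and 12/48 at n = 60; 12/12 at n = 24. The 12/48 and 12/12 splits are assumptions.
- *Metabolites.* Assumed 50 to 400, either independent or in blocks of 10 with correlation 0.5.
- *Level.* 0.05 (Protocol 9.4).

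**3. OPLS on pure noise**

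One predictive and one orthogonal component, autoscaled, 100 data sets per setting, with seven-fold cross-validation for comparison. Means for n = 60, split 30/30, shown as independent / correlated metabolites:

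| Metabolites | In-sample AUC | In-sample R² | Cross-validated AUC | Q² |
|---|---|---|---|---|
| 50 | 0.964 / 0.898 | 0.628 / 0.453 | 0.496 / 0.471 | -0.653 / -0.524 |
| 100 | 0.999 / 0.969 | 0.830 / 0.639 | 0.480 / 0.477 | -0.568 / -0.570 |
| 200 | 1.000 / 0.997 | 0.944 / 0.795 | 0.500 / 0.486 | -0.294 / -0.503 |
| 400 | 1.000 / 1.000 | 0.983 / 0.909 | 0.472 / 0.494 | -0.186 / -0.340 |

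With a 12/48 split, in-sample AUC is 0.94 to 1.00 and cross-validated AUC 0.47 to 0.50. With n = 24 they are 0.99 to 1.00 and 0.41 to 0.49. Over all settings the cross-validated AUC lies between 0.41 and 0.50 and Q² is negative, so the separation vanishes once patients are held out.

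**4. Per-metabolite tests at 0.05**

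Expected false positives = m × 0.05. The chance of at least one = 1 − 0.95^m, which assumes independence; the expected count does not.

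| m | Expected false positives | At least one |
|---|---|---|
| 50 | 2.5 | 92% |
| 100 | 5 | 99.4% |
| 200 | 10 | >99.99% |
| 400 | 20 | >99.99% |

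These are per outcome and per time point. Tukey HSD does not help: it adjusts pairs of groups within one metabolite, and with two outcome groups there is only one pair.

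**The case against.** The strongest reply is SAP 8.9. Details sit in a separate document that is not available here, and it may well contain validation and multiplicity rules. A reader might infer that the sponsor has chosen an unvalidated fit and unadjusted tests. The documents do not support that: they are silent on both, and silence is not a decision. What remains is that 9.9 names its methods down to the software version yet gives neither rule and points to no further plan, whereas 9.8 does refer to a population PK analysis plan.

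A reader might also infer that the analysis relies on OPLS and will report a biomarker whether or not one exists. That too goes beyond the text. PCA, univariate tests and pathway mapping are planned beside OPLS, its stated use is dimension reduction and visualisation, and no patient selection or go/no-go rule hangs on it. But a display of clustering by outcome is exactly what a supervised fit produces from noise, so calling it visualisation does not remove the risk.

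Finally, a reader might infer that only baseline will be analysed and the Day 8 data wasted. The SAP keeps the pre/post endpoint, 9.2 says intra-patient and 9.9 lists a paired test, so change was probably intended. That favours reading the conflict as faulty wording, but the wording stands in the endpoint definition and the analysis section, and no paired comparison is defined anywhere.

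To call the analysis merely exploratory is only a partial answer: the documents list metabolomics as a secondary objective and endpoint and apply the word exploratory to the pharmacogenomic and pharmacogenetic substudy.

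**Conclusion.** The point holds in two parts of different certainty. The endpoint conflict is plain from the text: 9.2 and the first sentence of 9.9 disagree with the objective, the synopsis, 1.3, 7.9 and SAP 3.3, and should be corrected whatever the separate document says.

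The second part is a gap in the supplied documents, not a demonstrated fault in the final analysis. If the methods in 9.9 were applied with nothing added, an in-sample OPLS fit would show AUC of about 0.90 to 1.00 on noise over the assumed range of 50 to 400 metabolites, against roughly 0.5 or below when cross-validated, and the univariate tests would give about 2.5 to 20 false positives per outcome and time point. The direction does not depend on the metabolite count or correlation, both of which are assumed; the size does, and near-perfect separation at n = 60 should not be quoted for the low end of the range. The primary endpoint and the 25-of-60 rule are unaffected. The changes should be made, but nothing in the conduct of the trial turns on them.

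**What to change.** 1. In Protocol 9.2 and the first sentence of 9.9, replace *pretreatment* by *pre- and post-treatment*. State that within-patient change from Cycle 1 Day 1 to the Day 8 samples of Cycles 1 and 2 is analysed alongside the baseline profile, and which paired test applies.
2. In 9.9, or in the separate document mentioned in SAP 8.9, require cross-validated OPLS performance (Q² or AUC) with a permutation p-value beside any OPLS plot.
3. In the same place, give the number of metabolites and apply false-discovery-rate control across them within each outcome and time point. Benjamini-Hochberg is one suitable choice.
4. If the rules go in the separate document, name it in 9.9 and SAP 8.9.

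The cost is wording, a little more analysis code and fewer nominally significant metabolites. No new samples are needed.
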